### **13.0 Withdrawal of Subjects**

Subjects who repeatedly fail to attend scheduled visits or do not complete the 10-week intervention within 12 weeks may be withdrawn by the investigator. Subjects who are or become medically unstable may be withdrawn by the investigator.

A subject may choose to stop the project at any point in time. He/she may choose to reschedule or stop participation altogether. For those who are withdrawn by the investigator, or those who voluntarily withdraw from the study, their data collected up to that point may be used by the investigator.

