## 10.0 Study Design / Methods

**Design:** This is a quasi-experimental, single group pilot study that investigates the impact of integrating cognitive rehabilitation into an 8-week OT-led activity- and participation-based stroke telerehabilitation program. Participants will attend a total of 15 study visits over 10 weeks. A summary and timeline of procedures are outlined and described in the following table.

**Visit Schedule:** To accommodate participant preference/comfort and feasibility, we have designed the visit schedule to be flexible in the following ways:

- The PRE assessment visit will occur within 1-10 days prior Telerehab session 1 and the POST assessment visit will occur within 1-10 days after Telerehab session 13.

- Given the 2–3-hour length of the PRE session, the participant and therapist may decide to split the PRE procedures over 2 visits if the participant becomes fatigued or has other time constraints.
- We will make an effort to schedule telerehab visits on the days and times of the participants' choosing to the extent that the therapists' schedules permit.
- In extenuating circumstances that lead to cancellations/missed sessions (e.g., serious weather event, illness, holidays):
  - Telerehab sessions may extend into an additional week. This would make the intervention duration 9 weeks instead of 8 and the duration of full participation 11 weeks instead of 10.
  - Make-up telerehab sessions may be added to any intervention week.

Week	Week 1	Weeks 2-3	Weeks 4-6	Weeks 7-9	Week 10
Session	PRE	1-4	5-10	11-13	POST
Mode (session duration)	Virtual (2-3 hrs)	Telerehab (45–75 min/session 2x/week)	Telerehab (45–75 min/ session 2x/week)	Telerehab (45–75 min/session 1x/week)	Virtual (2 hrs)

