### Session “POST”: POST-TREATMENT ASSESSMENTS

**Outcome Measures:** We will repeat the same measures administered at pre-treatment to assess cognition (objective and subjective), functional task performance, activity participation, and psychosocial function:

Outcome Domain	Instrument
Cognition	MoCA
Cognition	NeuroQoL-Cognitive Function Short Form v.2.0
Functional Task Performance and Activity Participation	Patient Specific Functional Scale (PSFS)
Functional Task Performance and Activity Participation	Performance Quality Rating Scale (PQRS) a
Functional Task Performance and Activity Participation	Stroke Self Efficacy Questionnaire (SSEQ)
Psychosocial Function	Patient Health Questionnaire (PHQ-9) b
Psychosocial Function	Inventory of Psychosocial Functioning
Psychosocial Function	PROMIS Sleep Disturbance

aThe PQRS will not be administered at the PRE and POST visits and instead will be administered at actual telerehab visits to more proximally assess function. Specifically, it will be administered at the beginning of the first telerehab visit (session 1), the beginning of the first visit with OT (session 5), and at the end of the last telerehab visit (session 13).

bThe Columbia Suicide Severity Rating Scale (C-SSRS) will also be administered if suicidal ideation/intent is endorsed (as described in Section 12.0).

**Telerehab Experience Survey:** At the POST visit, participants will complete two brief surveys regarding their experiences of completing the telerehabilitation program, the Acceptability of Intervention Measure (AIM) and the Intervention Appropriateness Measure (IAM). They will also have the option to provide narrative, qualitative responses about what they liked and did not like about the program. The survey will be administered via Redcap.

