## 11.0 Data Management

**Recruitment Data:** Recruitment records will be housed in REDCap. Only IRB-approved study personnel will have access to the REDCap database while actively enrolling for the study.

Data Analysis: Data from the prospective sample (n=20) will be used to calculate descriptive statistics of all outcome measures collected prior to (pre-treatment) and immediately following (post-treatment) the intervention and the corresponding change scores. The preliminary effect sizes of the proposed intervention will be generated by evaluating 1) change in each outcome measure from pre- to post-treatment and 2) the associations between changes in cognitive measures and changes in the participation and psychosocial function measures. To explore the potential additive benefit of cognitive priming, we will compare change in the participation measures between the prospective sample (n=20) and historical data (n=30) from stroke survivors who have completed the telerehabilitation program without the cognitive rehabilitation primer component.

Confidentiality: All data except for the consent forms and HIPPA forms will be coded at the time of data recording. All electronic data will be stored in a password-protected research server that is accessible to IRB-approved study personnel only. All paper data with personally identifiable information (e.g., the consent forms) will be stored in a key-locked cabinet in a key-locked room that is accessible to IRB-approved study personnel only. Other paper data without personally identifiable information including testing sheets documenting testing sequences and notes will also be stored in a cabinet in a key-locked room that is accessible to IRB-approved study personnel only.

Data sharing: Only de-identified coded data will be reported and/or shared with the public and other investigators in publications, in ClinicalTrials.gov, or via data depository.

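### Poor or late attenders may be withdrawn with no provision for a POST assessment, so the effect estimates and acceptability ratings can come only from those kept to POST

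*Combined protocol and SAP*

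**What the plan says.** Section 13.0 (Withdrawal of Subjects) gives the trigger: "Subjects who repeatedly fail to attend scheduled visits or do not complete the 10-week intervention within 12 weeks may be withdrawn by the investigator". For people withdrawn by the investigator, and for those who leave of their own accord, it adds that "their data collected up to that point may be used by the investigator".

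Section 10.0 ties the final assessment to the last session: "the POST assessment visit will occur within 1-10 days after Telerehab session 13". Under the POST heading, the AIM and IAM are placed at that visit: "At the POST visit, participants will complete two brief surveys regarding their experiences of completing the telerehabilitation program". The visit schedule allows make-up sessions and one extra week, of which it says: "This would make the intervention duration 9 weeks instead of 8 and the duration of full participation 11 weeks instead of 10".

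Section 11.0 (Data Analysis) bases the preliminary effect sizes on "change in each outcome measure from pre- to post-treatment" and describes the sample without reference to attrition: "Data from the prospective sample (n=20) will be used to calculate descriptive statistics of all outcome measures". The exploratory comparison uses 30 historical patients, described as "stroke survivors who have completed the telerehabilitation program without the cognitive rehabilitation primer component".

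**The concern.** The rule links study participation to attendance. Once a person is withdrawn, nothing in the protocol provides for a later POST assessment or exit survey. The word used for the attendance trigger has no threshold, and the decision rests with the investigator, so the selection step is undefined as well as discretionary.

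The protocol's own reasoning makes the loss plausibly informative. The Background (Section 2.0) says that executive dysfunction may hinder engagement in rehabilitation and describes the programme as cognitively demanding. Those most likely to miss sessions may therefore be the people the cognitive primer is meant to help.

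Two products of the pilot are at stake. The effect estimates are intended to inform larger trials (Section 1.0), and an estimate restricted to those kept to POST could be taken for the effect in everyone enrolled. The AIM and IAM ratings would also omit the people who could best explain why the programme did not suit them.

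**Working it through.** **What a withdrawn participant contributes**

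| Item | When collected | Available after withdrawal before POST? |
|---|---|---|
| MoCA, NeuroQoL, PSFS, SSEQ, PHQ-9, Inventory of Psychosocial Functioning, PROMIS Sleep Disturbance | PRE and POST | PRE value only, so no change score |
| PQRS | Sessions 1, 5 and 13 | A session 1-to-5 change if session 5 was reached; no change to session 13 unless that session was attended |
| AIM, IAM, narrative feedback | POST | No |
| Perceived usefulness of each cognitive skill | Session 4 | Yes, if session 4 was reached |

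I found no analysis set, missing-data method, dropout allowance or replacement rule that would change this picture.

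**Illustration of size**

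The plan gives N = 20 (Section 6.0) but no dropout rate, SD, expected change, alpha or power, so it has no figure to reproduce. The inputs below are assumptions, apart from the 20.

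Let w be the number without POST, dc the mean gain of those kept, and dw the mean gain of those withdrawn, in SD units of change.

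- All-enrolled mean = [(20 − w) × dc + w × dw] / 20.
- Overstatement = dc / (all-enrolled mean) − 1. With dw = 0 this reduces to 20 / (20 − w) − 1.
- 95% CI half-width = t(0.975, m − 1) / √m, with m = 20 − w.

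With dc = 0.50:

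| w | m | All-enrolled mean, dw = 0.50 | dw = 0 | dw = −0.30 | Half-width (SD) |
|---|---|---|---|---|---|
| 0 | 20 | 0.50 | 0.50 | 0.50 | 0.47 |
| 2 | 18 | 0.50 (0%) | 0.45 (11%) | 0.42 (19%) | 0.50 |
| 4 | 16 | 0.50 (0%) | 0.40 (25%) | 0.34 (47%) | 0.53 |
| 6 | 14 | 0.50 (0%) | 0.35 (43%) | 0.26 (92%) | 0.58 |

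Percentages in brackets are the overstatement. For example, with w = 4 and dw = 0: (16 × 0.50 + 4 × 0) / 20 = 0.40, and 0.50 / 0.40 − 1 = 25%. If those withdrawn had gained more than those kept, the sign would reverse. The wider interval follows from any attrition and is not specific to this rule.

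**The time limit**

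Section 13.0 refers to a 10-week intervention. Section 3.0 describes an 8-week intervention inside a 10-week study, and Section 10.0 allows 9 weeks of intervention and 11 weeks of participation. What the 12 weeks count makes a difference:

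- From PRE to POST, with both assessment windows at their maximum and the permitted extension: 10 + 9 × 7 + 10 = 83 days, against 12 × 7 = 84 days. That leaves one day of slack.
- For the intervention alone: 12 − 9 = 3 weeks of slack.

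Who counts as late therefore depends on a reading that the text does not settle.

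**Historical comparison**

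The 30 historical patients are described as having completed the earlier programme. If the new sample is in effect limited to those kept to POST, both sides are conditioned on completion, possibly under different rules.

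**The case against.** The strongest reply is that the rule is permissive. Withdrawal is an option, participants may reschedule, make-up sessions can be added to any intervention week, and an extra week is allowed. Poor or late attenders can therefore reach POST and be counted. This stands. A reader might infer that the results will come only from people who coped with the programme, but the documents support only that they can.

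Second, some information survives withdrawal: the early PQRS change and the session 4 usefulness ratings. This also stands. Neither replaces a full pre-post change or an AIM or IAM rating.

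Third, a reader might infer that the effect is biased upward by 11% to 43%. The documents do not show this. Those figures follow from assuming no gain in the people withdrawn. The examples Section 10.0 gives for missed sessions are weather, illness and holidays, which need not relate to cognition. Informative loss remains plausible on the Background's reasoning, but no more than that.

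Fourth, the sentence on data from withdrawn participants permits their use. It does not define a completer analysis, and Section 11.0 speaks of the whole sample of 20. This is fair, although permission to use partial data does not create a POST value.

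Fifth, a reader might see several conflicting durations. The 8- and 10-week figures agree with each other, as do 9 and 11. The one real mismatch is the length that Section 13.0 gives to the intervention.

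Finally, this is a single-group pilot with preliminary effect sizes and no confirmatory test. That limits the severity but does not remove the gap.

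**Conclusion.** The point holds in a limited form. As written, Section 13.0 allows participants to be withdrawn for poor attendance or lateness, and nothing provides for collecting their POST outcomes. Anyone withdrawn this way has no pre-post change score, apart from a possible session 1-to-5 PQRS change, and no AIM or IAM rating.

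The direction and size of any bias are unknown from the documents. The overstatement is zero if those withdrawn would have gained as much as the others. It is 11%, 25% or 43% for 2, 4 or 6 losses if they gained nothing, and larger if they worsened. All of these rest on assumed gains and assumed numbers of withdrawals.

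I rate this a worthwhile, inexpensive improvement rather than a correction the study cannot do without. It is best made early, because a missed POST cannot be recovered and each participant is 1/20 = 5% of the sample.

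**What to change.** - **Section 13.0.** Separate stopping the intervention from stopping outcome collection. Invite everyone who stops attending or runs late to the planned remote POST assessment and the AIM and IAM surveys, unless they withdraw consent. Give that POST a time anchor that does not depend on reaching session 13. State that data collected before withdrawal will be used where consent allows.
- **Section 11.0.** Define the main analysis set as all enrolled participants with a PRE assessment, using every available POST. Show completers as a secondary set, which is also the closer match to the historical group. Report the number of withdrawals and the reasons. Because this remains an available-case analysis, a short sensitivity table over assumed gains for those without POST, like the one above, would help readers.
- **Sections 3.0, 10.0 and 13.0.** Reconcile the stated length of the intervention and make clear what the 12-week limit counts.

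The cost is protocol wording and a few extra remote visits of about 2 hours each: 2 to 6 such visits would take 2 × 2 = 4 to 6 × 2 = 12 hours. No new procedure is needed. Some of those invited will decline, so the selection is reduced but not removed.

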### **14.0 Risks to Subjects**

There is a minor risk of mental and/or physical fatigue from engaging in the cognitive rehabilitation and occupational therapy rehabilitation intervention. There is also a risk of falling during the occupational therapy sessions. There is a risk that stroke survivors may experience sadness, fear, or anger if they have difficulty with the assessments or intervention because they may develop a greater realization of their deficits. It is also possible that the task-practice sessions result in temporary muscle soreness or fatigue. These risks to participants are no more than a usual-care stroke rehabilitation assessment and/or intervention session.

There is a risk of a loss of confidentiality of personal information that is used in this study although researchers will take appropriate steps to protect any information collected about the participants.

## 15.0 Potential Benefits to Subjects or Others

There may be no benefit from participating in this study. The potential benefit is that the telerehabilitation program (cognitive rehabilitation in combination with measurement-based task practice with metacognitive strategy training) will promote participants' recovery of paretic arm/hand function, although this cannot be guaranteed. The knowledge regarding the potential of using this measurement-based method to improve function and activities of daily living for people who had a stroke may benefit stroke survivors in general.

## 16.0 Sharing of Results with Subjects

If a subject requests a copy of the assessment results, a printed copy of the results will be mailed or emailed to him/her.

If the subject agrees, the data collected and generated from this study will be shared to the Registry for Stroke Recovery (RESTORE-Pro#00037803) by the subject's registry ID. Sharing data from this study with the registry will allow for more targeted recruitment efforts in the future and allow researchers at MUSC to have a more complete registry with key stroke recovery elements including common data and physical function characteristics that are applicable to multiple studies. MUSC researchers and collaborating facilities will be able to query data sets to learn more about recovery of subjects after their stroke through institutionally managed secure servers that will assure HIPAA privacy and security compliance.

